In Parts 1A, 1B, 2A, and 2B, the initial treatment period is up to 24 weeks (3 cycles) of dosing and the number of 8-week cycles will depend on tumor assessment at each cycle. Following each treatment cycle, the decision to treat a participant with the next cycle of study therapy, up to a maximum of 48 weeks (6 cycles) of treatment, will be based on safety/benefit and tumor assessment. For Parts 1C and 2C, the treatment period is up to a maximum of 2 years in the absence of disease progression or unacceptable toxicity. Upon completion of these treatment, participants will enter a safety follow-up period.

Details of the dose escalation and cohort expansion phase in this study are given in the study design section and the schematic above. For Parts 1A, 1B, 2A and 2B intra-participant dose escalation/reduction of BMS-986207, nivolumab, or ipilimumab is not permitted in this study in order to allow better evaluation of the extended safety and efficacy at individual dose levels and schedules. For intra-participant dose reduction of BMS-986207 in Part 1C and 2C see [Section 5.1.2.6](#) and [Section 5.1.2.7](#), respectively.

Study treatment will be dispensed at the study visits. For participants on combination treatment, a 30-minute infusion of nivolumab will be followed by a 30-minute observation period, followed by a 60-minute infusion of BMS-986207, with a 60-minute observation period after all infusions in Cycle 1 for each participant. For participants < 42 kg receiving the 1600-mg dose of BMS-986207 or <38 kg receiving the 1200-mg dose of BMS-986207, the infusion time will be longer than 1 hour. For participants in Part 1C or Part 2C, a 30-minute infusion of nivolumab will be followed by a 30-minute observation period; followed by a 30-minute infusion of ipilimumab, a 30-minute observation period, and by a 60-minute infusion of BMS-986207.

Treatment Assignment: In this open-label study, no blinding will be required. Enrolled participants will be assigned sequential participant numbers via IRT starting with [REDACTED] (eg, [REDACTED]). Enrolled participants meeting the inclusion criteria will be eligible to be dosed. In the expansion phase only, participants with CRC will be randomized in a 1:1 manner to either BMS-986207 monotherapy or combination therapy with BMS-986207 and nivolumab to eliminate the possibility of enrollment bias.

STUDY ASSESSMENTS AND ANALYSES:

Safety Assessments: Safety assessments will be based on reported AEs and the measurement results of vital signs, ECGs, physical examinations, and clinical laboratory tests. AEs will be coded using the most current version of the Medical Dictionary for Regulatory Activities (MedDRA) and the incidence of observed AEs will be tabulated and reviewed for potential significance and clinical importance. AEs will be assessed continuously during the study and for 100 days after the last dose of BMS-986207 in the case of monotherapy, and the last dose of BMS-986207 and nivolumab, and the last dose of BMS-986207, nivolumab, and ipilimumab for combination therapy. A central/local laboratory will perform the clinical laboratory tests and will provide reference ranges for these tests. Both AEs and laboratory tests will be graded using the National Cancer Institute Common Terminology Criteria for Adverse Events v4.03.

PK Assessments: Pharmacokinetics of BMS-986207 will be derived from serum concentration versus time data. The pharmacokinetic parameters that will be assessed, following the intensive PK collection, are: maximum observed serum concentration (Cmax), time of maximum observed serum concentration (Tmax), area under the plasma concentration-time curve (AUC) from time zero to the time of the last quantifiable concentration (AUC[0-T]), AUC in 1 dosing interval (AUC[tau]), observed concentration at the end of a dosing interval (Ctau), total body clearance (CLT), average concentration over a dosing interval (Css-avg), accumulation index (AI), effective elimination half-life that explains the degree of accumulation observed for a specific exposure measure (T-HALFeff), [REDACTED]
[REDACTED]. Individual participant PK parameter values will be derived by noncompartmental methods by a validated PK analysis program. Actual times will be used for the analyses.

Immunogenicity Assessments: Serum samples for BMS-986207, [REDACTED] anti-drug antibody (ADA) will be collected from all participants at specified time points.
[REDACTED]

Efficacy Assessments: Efficacy assessments for the [REDACTED] activity of BMS-986207, alone, in combination with nivolumab, or in combination with nivolumab and ipilimumab will be based on tumor measurements, using RECIST v1.1, with computer tomography and/or magnetic resonance imaging, as appropriate, at baseline, every 8 weeks (\pm 1 week) for Parts 1A, 1B, 2A, and 2B or every 6 weeks for Part 1C and Part 2C during the treatment period, and every 12 weeks thereafter during the response follow-up period.

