The DLT period in Part 1C will be 42 days (6 weeks). The DLT safety monitoring during the dose evaluation phase, including the potential decision to de-escalate to a lower dose, will be based on the Bayesian optimal interval (BOIN) design framework with a dose-limiting toxicity (DLT) rate of 30% (24%, 36%).

Subjects who do not complete the DLT observation period for reasons other than DLTs may be replaced. De-escalation may be considered if the safety and tolerability profiles for the selected BMS-986207 dose are deemed unacceptable, after discussion between the investigator (s) and the Sponsor/Medical Monitor.

Cohort Expansion (Part 2A, 2B, and 2C): In the cohort expansion part of the study, additional safety, tolerability, preliminary efficacy, PK, [REDACTED] information, regarding BMS-986207 alone and in combination with nivolumab, will be sought. Continuous evaluation of toxicity events will be performed throughout enrollment in the expansion cohorts. If, at any time, the aggregate rate of treatment-related toxicities meeting DLT criteria exceeds 33% across all participants treated in cohort expansions, reassessment of enrollment will take place. Depending on the nature and grade of the toxicity and after assessing the risk/benefit ratio, a new dose(s) for all cohorts may be initiated at a previously tested lower dose level or at a dose level intermediate to previously tested lower dose levels.

In Part 2A, only CRC will be evaluated in cohort expansion with BMS-986207 as monotherapy. In Part 2B, the 3 disease-restricted populations, ovarian cancer, CRC and HCC, will be investigated in cohort expansions with BMS-986207 in combination with nivolumab. A Fleming 2-stage design framework will be used as a guide in cohort expansion.

During the expansion phase, participants with CRC who have disease progression on BMS-986207 monotherapy will be able to cross over to combination treatment (BMS-986207 + nivolumab), once the CRC expansion arms are enrolling. This cross-over option is not applicable during the escalation phases. CRC participants with disease progression who cross over to combination treatment will undergo the same efficacy and safety assessments as the main cohort.

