The purpose of Part 2C is to gather preliminary efficacy information regarding BMS-986207 in combination with nivolumab and ipilimumab in participants with advanced, treatment-naïve NSCLC whose tumors express [REDACTED] to assess optimal dose selection for RP2D. These subjects will be treated with BMS-986207 q3w at a dose not to exceed the dose declared tolerable in Part 1C, nivolumab 360 mg q3w, and ipilimumab 1 mg/kg q6w. Additional doses lower than the dose declared tolerable might be tested for dose optimization in Part 2C.

Part 2C may begin once there is sufficient safety data from a minimum of 6 participants in Part 1C.

Continuous evaluation of toxicity events will also be performed in this part of the study. If, at any time, the aggregate rate of treatment-related toxicities meeting DLT criteria exceeds 33%, the findings will be discussed and further enrollment may be interrupted. Depending on the nature and grade of the toxicity, and after assessing the risk/benefit ratio, a new dose for all participants may be initiated at a lower dose level.

Participants with an outcome of unconfirmed progressive disease, stable disease (SD), partial response (PR), or complete response (CR) at the end of a given cycle will continue to the next treatment cycle. Participants will be allowed to continue study treatment until the first occurrence of either: 1) completion of the maximum number of cycles, 2) confirmed PD, 3) clinical deterioration suggesting that no further benefit from treatment is likely, 4) intolerance to therapy, or 5) the participant meets criteria for discontinuation of study therapy. Individual participants with confirmed CR will be given the option to discontinue study therapy on a case-by-case basis after specific consultation and agreement between the investigator and BMS Medical Monitor in settings where benefit/risk justify discontinuation of study therapy.

Dose Limiting Toxicities: For the purpose of guiding dose escalation, DLTs will be defined based on the incidence, intensity, and duration of adverse events (AEs) for which no clear alternative cause is identified. DLT period will be 28 days (4 weeks) in Part 1A and Part 1B and 42 days (6 weeks) in Part 1C.

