5.1.2.7 Cohort Expansion (Parts 2A, 2B, and 2C)

The purpose of cohort expansion is to gather additional safety, tolerability, preliminary efficacy, PK, [REDACTED] information regarding BMS-986207 alone and in combination with nivolumab. Continuous evaluation of toxicity events in the cohort expansions will be performed throughout enrollment in the expansion cohorts. If, at any time, the aggregate rate of treatment-related toxicities meeting DLT criteria exceeds 33% across all participants treated in cohort expansions 2A or 2B, the findings will be discussed and further enrollment will be interrupted. Depending on the nature and grade of the toxicity, and after assessing the risk/benefit ratio, a new dose for all cohorts may be initiated at a previously tested lower dose level or at a dose level intermediate to previously tested, lower dose levels.

In Part 2A, only CRC will be evaluated in cohort expansion with BMS-986207 as monotherapy. In Part 2B, the 3 disease-restricted populations, ovarian cancer, colorectal cancer (CRC) and HCC will be investigated in cohort expansions with BMS-986207 in combination with nivolumab. A Fleming 2-stage design framework will be used as a guide in cohort expansion.

During the cohort expansion phase, participants with CRC who have disease progression on BMS-986207 monotherapy will be able to cross over to combination treatment (BMS-986207 + nivolumab), once the CRC expansion arms (ie, monotherapy and combination therapy) are both enrolling. This cross-over option, for CRC participants only, is not applicable during the escalation phases.

The purpose of Part 2C is to gather preliminary efficacy information regarding BMS-986207 in combination with nivolumab and ipilimumab. Participants with advanced, treatment-naïve NSCLC whose tumors express PD-L1 will be treated with BMS-986207 in combination with nivolumab and ipilimumab. BMS-986207 will be administered at 600 mg q3w (or tolerable dose as determined in Part 1C) and nivolumab will be administered at 360 mg q3w. Ipilimumab, at a dose of 1 mg/kg, will be given q6w.

Part 2C may begin once there is sufficient safety data from a minimum of 6 participants in Part 1C.

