Part 2C will enroll a minimum of 20 participants per dose level of BMS-986207. One or two doses are planned to be evaluated and selected from the range of doses assessed as tolerable and not exceeding the maximum tolerated dose in Part 1C. If two doses will be tested at the Sponsor's discretion, participants will be randomized in a 1:2 ratio schema between the highest dose selected in Part 1C and the next lower dose, after at least 10 participants will have been tested at the dose found safe in Part 1C.

Continuous evaluation of toxicity events will also be performed in this part of the study. If, at any time, the aggregate rate of treatment-related toxicities meeting DLT criteria exceeds 33% in Parts 2A or 2B, the findings will be discussed and further enrollment may be interrupted. In addition, a more guided continuous safety monitoring will be implemented in Part 2C, 1L NSCLC expansion, using a Bayesian framework and specific criteria based on a posterior probability of a DLT rate exceeding 33% implemented starting with n=6 ([Table 10.3.8-1](#)). Depending on the nature and

grade of the toxicity, and after assessing the risk/benefit ratio, a new BMS-986207 dose for all participants, including those currently on treatment, may be initiated at a lower dose level.

Participants with an outcome of unconfirmed progressive disease, stable disease (SD), partial response (PR), or complete response (CR), at the end of a given cycle, will continue to the next treatment cycle. Participants will be allowed to continue study treatment until the first occurrence of any of the following:

- Completion of the maximum number of cycles
- Confirmed PD (see [Section 5.1.4](#))
- Clinical deterioration suggesting that no further benefit from treatment is likely
- Intolerability to therapy
- Participant meets criteria for discontinuation of study treatment as shown in [Section 8.1](#)

5.1.2.8 *Treatment with Additional Cycles Beyond 24 Weeks (Parts 1A, 1B, 2A, and 2B)*

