5.1.5 Data Monitoring Committee and Other External Committees

BMS has developed a multi-layered process to ensure safety monitoring through close collaboration of study site Investigators, the BMS study team, and the BMS Worldwide Patient Safety (WWPS)-led Safety Management Team (SMT). This collaborative process constitutes the safety-monitoring plan for the study. To support safety oversight, BMS has established ongoing processes for collection, review, analysis, and submission of individual adverse event reports and their aggregate analyses. Because this is an open-label study, WWPS, the BMS Medical Monitor, and the Investigators will have access to all data necessary for safety evaluation.

BMS WWPS is an internal group that operates independently from the clinical team to monitor safety across all BMS protocols and analyze all accumulated safety data. Within BMS, an SMT is established for investigational therapies under clinical development, and a member of WWPS chairs this team. In addition, safety signal detection is performed at least monthly and ad hoc throughout the study by the SMT composed, at a minimum, of the WPS medical safety assessment physician (Chair of the SMT) and WWPS single-case review physician, the study Medical Monitor, the study biostatistician, and epidemiologist, all of whom evaluate the safety data regularly. Furthermore, the SMT routinely monitors for actual or potential issues related to participant safety that could result in a change in the medical benefit-risk balance associated with the use of study treatment(s). For Part 2C, continuous safety monitoring based on a Bayesian framework is also planned in the NSCLC cohort for ongoing evaluation of the tolerability of the selected dose.

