10.3.2 Safety Analyses

All safety analyses will be performed on the treated population.

Endpoint	Statistical Analysis Methods
Incidence of DLTs, AEs, SAEs, AEs leading to discontinuation, and death AEs will be graded according to CTCAE v4.03	DLT rate by dose level, frequency distribution of treated participants with AE using the worst CTC grade. Participants will only be counted (1) once at the PT level, (2) once at the system organ class level, and (3) once in the 'total participant' row at their worst CTC grade, regardless of system organ class or PT.
Laboratory abnormalities Laboratory values will be graded according to CTCAE v4.03.	Laboratory shift table using the worst CTC grade on treatment per participant

Abbreviations: AE, adverse event; CTC, common terminology criteria; CTCAE, common terminology criteria for adverse events; DLTs, dose-limiting toxicities; PT, preferred term; SAE, serious adverse event.

In addition, continuous safety monitoring for toxicity will be conducted in the NSCLC Expansion Phase 2C as described in [Section 10.3.8](#).

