10.3.8 Interim Analyses for Parts 2A, 2B, and 2C

The expansion phase of this study (Part 2A and Part 2B) employs a 2-stage design framework. Therefore, there will be an interim analysis as planned when an adequate number of participants have response-evaluable data. Additional interim analyses may also be performed for administrative purposes or publications. No formal inferences requiring any adjustment to statistical significance level will be performed.

For Part 2C, interim analyses may also be performed for administrative purposes or publications prior to the final database lock. No formal inferences requiring any adjustment to statistical significance level will be performed. Continuous safety monitoring will be implemented in Part

2C to further evaluate the safety of the triplet combination in the NSCLC population, in addition to that in Part 1C, as described below.

A Bayesian framework will be utilized for continuous monitoring of toxicity in Part 2C based on AEs meeting DLT criteria.⁴⁶ Observed incidence rates of treatment-related toxicities meeting DLT criteria (defined in [Section 7.4.1](#)) will be evaluated relative to a boundary (number of DLTs) associated with higher chance of the true DLT rate exceeding 33%.

Bayesian safety monitoring boundaries are established using a non-informative prior, Beta (0.5, 0.5). The posterior distribution is Beta ($0.5+n$, $0.5+(m-n)$), where m is number of treated Part 2C participants and n is the subset of these m participants who experience treatment-related toxicities meeting DLT criteria. All treated Part 2C participants are considered evaluable. The criterion for excess toxicity is based on a posterior probability (PP) of treated Part 2C participants with toxicities meeting DLT criteria $> 33\% \mid$ cumulative data exceeding 80%. If the criterion is met during continuous monitoring in Part 2C, there is greater than 80% PP that the DLT rate exceeds 33%; based on the observed data, the dose level may be re-evaluated and, based on the totality of data, a lower dose may be administered to the remaining participants. The cutoff number of participants with DLT needed to meet the criterion depends on the number of evaluable participants, with a final boundary of 14 participants with a DLT out of 37 or more.

Table 10.3.8-1: Safety Monitoring Boundaries for AEs Meeting DLT Criteria in Part 2C

Number of evaluable participants	Minimum Number of participants with AE meting DLT criteria
4 -6	3
7-8	4
9-11	5

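### The Synopsis gives Part 2C a raw DLT-rate trigger above 33% that Section 5.1.2.7 reserves for Parts 2A and 2B, and the Part 2C boundary table does not match its own 80% criterion at half of its sample sizes

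*Combined protocol and SAP*

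**What the plan says.** **Synopsis, Cohort Expansion.** The general sentence, placed under a heading that covers Parts 2A, 2B and 2C, acts when the DLT-criteria rate "exceeds 33% across all participants treated in cohort expansions, reassessment of enrollment will take place". The later Part 2C paragraphs say that toxicity is also evaluated continuously in this part of the study and that, whenever "the aggregate rate of treatment-related toxicities meeting DLT criteria exceeds 33%, the findings will be discussed and further enrollment may be interrupted". Neither sentence is limited to particular parts. Neither gives a minimum number of participants or mentions a Bayesian rule.

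**Section 5.1.2.7.** Both matching sentences carry a limit. The general one reads "exceeds 33% across all participants treated in cohort expansions 2A or 2B, the findings will be discussed" and says enrollment will then be interrupted. The one after the Part 2C description reads "exceeds 33% in Parts 2A or 2B, the findings will be discussed and further enrollment may be interrupted". Part 2C is then given, in addition, "specific criteria based on a posterior probability of a DLT rate exceeding 33% implemented starting with n=6", with a reference to Table 10.3.8-1.

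**Other body sections.** Section 5.1.5: "For Part 2C, continuous safety monitoring based on a Bayesian framework is also planned in the NSCLC cohort". Section 10.3.2: "continuous safety monitoring for toxicity will be conducted in the NSCLC Expansion Phase 2C as described in" (the reference is to Section 10.3.8).

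**Section 10.3.8.** This defines the rule: a Beta(0.5, 0.5) prior, all treated Part 2C participants evaluable, and excess toxicity flagged when the posterior probability (PP) that the DLT rate exceeds 33% is above 80%. It says that when the criterion is met "there is greater than 80% PP that the DLT rate exceeds 33" per cent. It presents the table counts as those needed to meet the criterion, ending at 14 for 37 or more participants. The raw trigger is not mentioned.

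**The concern.** A reader who works from the Synopsis and one who works from Sections 5.1.2.7 and 10.3.8 would open a Part 2C safety discussion at different DLT counts. Safety is part of the Part 2C primary objective, and 2 of 4 DLT-evaluable participants had DLTs on this triplet at 1200 mg in Part 1C, so the threshold is likely to be consulted.

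Sending Part 2C to Section 10.3.8 does not fully settle the count either. That section offers a posterior criterion and a table as the same rule, and at many sample sizes they are not the same.

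**Working it through.** **Inputs.** From Section 10.3.8: prior Beta(0.5, 0.5), threshold 0.33, cutoff 0.80 and the printed table, with its last row (14) carried to 40 because the text says 37 or more. From Section 5.1.2.7: monitoring from 6 participants and at least 20 per dose level. From the Synopsis: a raw rate above 33%. Section 10.1.1 equates 33% with about 2 in 6, so I read the raw threshold both as 1/3 and literally as 0.33.

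**Formulas.** With k participants with a DLT among m treated:
- Raw trigger: smallest k with k/m above the threshold.
- Criterion trigger: smallest k with P(rate > 0.33) > 0.80 under Beta(0.5 + k, 0.5 + m − k).

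**The plan's own figure at m = 20.** 8/20 gives PP 0.752 and 9/20 gives 0.872, so the criterion needs 9, as printed. The raw rule is met at 7 (6/20 = 30%, 7/20 = 35%), where PP is only 0.585. The pair 7 and 9 is the same for both readings of 33%, and for table and criterion alike.

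**Bayesian count minus raw count, the 35 sizes from 6 to 40.**

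| Bayesian count | 33% read as 1/3 | 33% read literally |
|---|---|---|
| Printed table | 0 at 4 sizes (6, 36, 39, 40); 1 at 30; 2 at m = 20 only | 0 at m = 40; 1 at 24; 2 at 10 (9, 12, 15, 18, 20, 21, 24, 27, 30, 33) |
| Criterion (PP > 80%) | 0 at m = 6; 1 at 14; 2 at 20 | 1 at 8; 2 at 23; 3 at 4 (30, 33, 36, 39) |

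These counts apply to the Part 2C sentence only. The general Synopsis sentence describes a rate pooled over all expansion cohorts.

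**Table against criterion, the 36 sizes from 4 to 39.** They agree at 18 and differ at 18: m = 14, 17, 22, 23, 25, 26 and 28 to 39. The printed count is always the lower one, by 2 at m = 36 and 39 and by 1 elsewhere. Examples:
- 14/37: PP 0.738. The criterion needs 15 (0.836).
- 14/39: PP 0.656. The criterion needs 16.

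**Chance of at least one flag.** Exact recursion, assuming independent DLTs and a look after every participant from the 6th, with raw 33% read as 1/3. The true rates are assumptions; 30% is the plan's Part 1C target.

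| True DLT rate | Participants | Raw | Table | Criterion |
|---|---|---|---|---|
| 20% | 20 | 0.272 | 0.137 | 0.131 |
| 30% | 20 | 0.611 | 0.399 | 0.381 |
| 33% | 20 | 0.703 | 0.494 | 0.474 |
| 20% | 40 | 0.287 | 0.152 | 0.135 |
| 30% | 40 | 0.682 | 0.519 | 0.434 |
| 33% | 40 | 0.785 | 0.650 | 0.552 |

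The raw column is sensitive to the reading. At 20% and 40 participants it is 0.287 as shown, 0.444 with literal 33%, and 0.498 with 1/3 but looks from the first participant, since the Synopsis sets no minimum.

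**The case against.** The strongest reply is that the two rules can coexist. The Synopsis trigger opens a discussion and may pause enrollment; the Section 10.3.8 boundary may lead to dose re-evaluation. Section 5.1.2.7 introduces the Bayesian rule as an addition, which sounds like layering. But the raw trigger in that same place is expressly tied to Parts 2A or 2B, so layering for Part 2C is not what it says. If layering was intended, the body needs the edit instead.

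A second reply is that the slip could lie in Section 5.1.2.7. A trigger for Parts 2A and 2B sits oddly after the Part 2C paragraphs, and the section is not tidy about that trigger: interruption is certain in one sentence and possible in the other. This part stands, and a reader should not infer that the body is free of inconsistency. On which rule Part 2C follows, however, Sections 5.1.2.7, 5.1.5, 10.3.2 and 10.3.8 all point to the Bayesian boundary.

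A third reply is that little depends on it. Section 5.1.5 provides safety signal detection at least monthly and ad hoc whatever the count, and neither trigger forces a stop. That stands and sets the severity.

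Finally, the table mismatch is a separate defect from the Synopsis wording. That is correct. It is included because the Synopsis fix would send readers to that section.

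**Conclusion.** The inconsistency holds, at minor severity. Two thresholds are in force for Part 2C, and at 20 participants they are 7 and 9 on any reading. Elsewhere the size depends on the reading. The printed table is 0 to 2 above the raw count, with a gap of 2 at m = 20 only or at ten sizes. The stated criterion is mostly 2 above it, and up to 3 if 33% is literal. A flat statement that the gap is usually 1 and never more than 2 would hold only against the printed table.

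Separately, reaching the printed count does not give more than 80% PP at 18 of 36 sizes, so Section 10.3.8 is wrong there as written.

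A reader might infer that participants lose protection. The documents do not support that: the raw rule is the more cautious, the printed counts are more cautious than the criterion at every mismatched size, both triggers are advisory, and ongoing safety review continues. Nor is any estimand, primary analysis or sample size affected. The flag probabilities are chances of opening a non-binding review under assumed true rates, not chances of stopping.

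**What to change.** **Synopsis.** Limit both raw 33% sentences (the general expansion sentence and the one in the Part 2C paragraphs) to Parts 2A and 2B, as Section 5.1.2.7 does. State that Part 2C follows Section 10.3.8 from 6 participants.

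**Section 10.3.8.** Choose one of two repairs:
- keep the printed counts as the governing rule, being the more cautious, and drop the claim that they correspond to more than 80% PP; or
- recompute the 18 mismatched entries and the final boundary of 14 for 37 or more from the stated criterion.

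The first option is a wording change. The second raises the counts at those sizes by 1 or 2. Either fits in the next amendment and changes no design, data collection or sample size. The one real downside is that the more cautious Synopsis trigger no longer applies to Part 2C. If the sponsor wants an early discussion trigger there, it should be added to Sections 5.1.2.7 and 10.3.8 explicitly, with a minimum number of participants.
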